1. Klatkiewicz, T., et al., Ultrasonography in the Diagnosis of Temporomandibular Disorders: A Meta-Analysis. Med Sci Monit, 2018. 24: p. 812-817.
2. Su, N., et al., Diagnostic value of ultrasonography for the detection of disc displacements in the temporomandibular joint: a systematic review and meta-analysis. Clin Oral Investig, 2018. 22(7): p. 2599-2614.
3. Melis, M., S. Secci, and C. Ceneviz, Use of ultrasonography for the diagnosis of temporomandibular joint disorders: a review. Am J Dent, 2007. 20(2): p. 73-8.

**PURPOSE OF THE RESEARCH** In the literature, there are not many studies on the diagnostic value of the use of ultrasonography in the diagnosis of temporomandibular joint diseases in dentistry. In this study, it is aimed to contribute to the literature in terms of revealing the reliability of the use of ultrasonography in the diagnosis of temporomandibular joint diseases.

**BENEFITS EXPECTED AT THE END OF THE RESEARCH** By revealing the efficacy and reliability of ultrasonography in the diagnosis of temporomandibular joint diseases, to eliminate the disadvantages of MR and other imaging methods.

**RESEARCH METHOD** Functional joint examination and ultrasonographic examination (USG) will be applied to all volunteers who will participate in the research. In the USG application, when the mouth is open and closed, the right and left joint intervals will be measured and a note will be taken. At the same time, right and left masseter muscle thicknesses will be measured separately at free-closing and tight-closing and a grade will be taken for all groups..

Volunteers to participate in the research will be divided into 4 groups.(I,II,III,IV).For volunteers in group 1 with previously taken MR images, USG and MR findings will be compared. In volunteers in group 2, the values obtained using different probes (linear, hockeystick) will be compared. In the third group of volunteers, the values to be obtained by using the USG probe at different angles (horizontal / longitudinal) will be compared. In volunteers in group 4, the megahertz values of the probe are changed and the findings obtained by examining them separately will be compared.

In addition to evaluating 4 groups separately, at the end of the research, USG data applied to all 4 groups will be

Protocol Information Form for Clinical Research	Doc. Code	Rev. Date/ No:	Page
	Form 3	13.06.2013/ÜDHFKA EK 00	2/6

analyzed by comparing all the findings obtained in functional joint examination.

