**WHICH STATISTICAL METHODS WILL BE EVALUATED**

In our study, SPSS application will be used for statistical analysis.

In evaluating the categorical variables, the Chi-Square test will be used to look for a difference between the groups. Normality control of continuous variables will be done with Kolmogorov-Smirnov test.

Difference evaluations of continuous variables between groups will be made with Student's t test in data with normal distribution. Group comparisons for data that are not suitable for normal distribution will be performed with Mann Whitney U test.

Descriptive statistics will be specified by giving mean, standard deviation, minimum and maximum values of all continuous variables. Frequency distributions and percentages of categorical variables will be specified.

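### The aim is the reliability of ultrasonography, but the statistics section names only independent-group difference tests and no measure of agreement or diagnostic accuracy

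*Combined protocol and SAP*

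**What the plan says.** The aim, under PURPOSE OF THE RESEARCH, is stated as follows: "it is aimed to contribute to the literature in terms of revealing the reliability of the use of ultrasonography". The title puts the same question.

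RESEARCH METHOD describes the measurements and comparisons:

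- Continuous USG measures: "In the USG application, when the mouth is open and closed, the right and left joint intervals will be measured". Masseter thickness is also measured, on each side and in two states of closure.
- Group 1: "For volunteers in group 1 with previously taken MR images, USG and MR findings will be compared". The findings are not defined.
- Group 2: "In volunteers in group 2, the values obtained using different probes (linear, hockeystick) will be compared". Groups 3 and 4 do the same for probe angle and probe frequency.
- All groups: USG data are set against the functional joint examination.

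The section WHICH STATISTICAL METHODS WILL BE EVALUATED names three tests. For categorical data: "In evaluating the categorical variables, the Chi-Square test will be used to look for a difference between the groups". For continuous data: "Difference evaluations of continuous variables between groups will be made with Student's t test in data with normal distribution", and "Group comparisons for data that are not suitable for normal distribution will be performed with Mann Whitney U test". It adds a Kolmogorov-Smirnov check, the mean, SD, minimum and maximum of continuous variables, and this: "Frequency distributions and percentages of categorical variables will be specified". It names no ICC, kappa, limits of agreement, measurement error, sensitivity, specificity or paired test, and neither does any other section reviewed.

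**The concern.** Each planned test asks whether groups differ or whether two classifications are associated. The question in groups 1 to 4 is how closely two readings of the same joint or muscle match, or how often USG gives the MR answer.

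For continuous measures, a t test or Mann-Whitney U can show at most a shift in location, and the independent-sample forms also discard the pairing. For categorical findings, chi-square on a USG-by-MR table detects association, but not its direction or the degree of agreement.

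A report that followed the plan exactly would therefore contain no estimate that answers the title question. The likely consequence is that p > 0.05 between two probes, or between USG and MR, is read as showing that USG is reliable.

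**Working it through.** **1. The plan's own figure.** SAMPLE INFORMATION uses f(α,β) = 7.85, SD 0.05 and a mean difference of 0.02. The two-sample formula gives 2 × 7.85 × (0.05/0.02)² = 2 × 7.85 × 6.25 = 98.1, which matches the stated 100 as a size per group. The one-sample or paired form gives 7.85 × 6.25 = 49.1 and does not match. So the sample size, too, rests on an unpaired difference in means.

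**2. Inputs for the illustrations.** The SD of 0.05 comes from SAMPLE INFORMATION (no unit given) and is taken here as the SD of each setting's values. Group sizes are not stated; an equal split of 100 over four groups gives 25 volunteers per group (assumed). Data are simulated as bivariate normal, 100,000 runs, two-sided 5% level.

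**3. Continuous data, equal means.** The limits of agreement are ±1.96 × √(2(1 − ρ)) × SD, where ρ is the correlation between settings.

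| ρ | Unpaired t non-significant | 95% limits of agreement |
|---|---|---|
| 0 (extreme: settings unrelated) | about 95% | ±1.96 × √2 × 0.05 = ±0.139 |
| 0.9 | over 99.9% | ±1.96 × √0.2 × 0.05 = ±0.044 |

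Mann-Whitney U gives the same two percentages. The limits differ about threefold (0.139/0.044 = 3.2), yet both situations would almost always be reported as showing no difference. The non-significance rates at equal means do not depend on the SD. The result at ρ = 0 does not depend on the 25 either: a 5,000-run check with unrelated standard normal data rejected in about 5% of runs at n = 25 and at n = 100.

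**4. Related defect: pairing ignored.** Take ρ = 0.9, SD 0.05 and a true shift of 0.02. The SD of the paired differences is 0.05 × √0.2 = 0.0224, with standard error 0.0224/√25 = 0.0045. The unpaired test works instead with 0.05 × √(2/25) = 0.0141. In simulation the unpaired t test misses the shift in about 92% of runs and the paired t test in about 1%.

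**5. Categorical data (extreme illustration, 50 joints).** USG-by-MR tables:

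- [20, 5; 5, 20]: observed agreement 40/50 = 0.80, expected 0.50, kappa = 0.30/0.50 = +0.60.
- [5, 20; 20, 5]: observed agreement 10/50 = 0.20, kappa = −0.30/0.50 = −0.60.

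For both, uncorrected chi-square = 50 × (400 − 25)²/25⁴ = 18.0, p = 2.2 × 10⁻⁵. If USG and MR are compared as positive rates instead (25/50 against 25/50), both give 0.0.

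**6. Precision of the replacement estimates, 25 volunteers assumed.**

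- ICC 0.80, two settings, one-way F method: F = 1.8/0.2 = 9. Lower: 9/2.242 = 4.01, (4.01 − 1)/(4.01 + 1) = 0.60. Upper: 9 × 2.257 = 20.3, 19.3/21.3 = 0.91.
- Each limit of agreement: 2.064 × √(1/25 + 1.96²/48) = ±0.72 SD of the differences.
- Sensitivity 20/25, with 25 MR-positive joints assumed: exact 95% CI 59% to 93% if joints are independent. At a within-volunteer correlation of 0.5 and worst-case pairing (design effect 1.5, effective n 16.7) it is about 54% to 95%.
- Kappa 0.60 on 50 joints: 0.60 ± 1.96 × √(0.8 × 0.2/(50 × 0.5²)) = 0.38 to 0.82, before clustering.

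**The case against.** Several points on the other side have force.

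- **Some planned analyses are informative.** A reader might infer that the whole plan can detect nothing beyond a mean shift. That is true only of the continuous measures. Chi-square on a USG-by-MR table detects association, and the promised frequencies would show raw agreement if cross-tabulated. The plan does not promise that table.
- **Functional examination.** A reader might extend the criticism to this comparison. Comparing joint interval or masseter thickness between volunteers with and without a clinical finding is a between-subject comparison, for which Student's t or Mann-Whitney U is legitimate.
- **The 0.02 in the sample-size section.** It is tempting to say that limits of ±0.044 or ±0.139 fail because they exceed 0.02. The documents give 0.02 as a mean difference for power, not as a tolerance for individual disagreement, and the SD comes from other dental studies without a unit. The limits are shown only to contrast two situations.
- **Reader reliability.** The text is silent on repeat readings within or between readers. That does not establish that none are planned.
- **Meaning of reliability.** The word may stand for diagnostic accuracy, since the same section speaks of diagnostic value. The gap remains, because no accuracy measure is named either.
- **Later repair.** Most agreement statistics could be computed afterwards from the same data. That is so, but the measures and the undefined group 1 findings would then be chosen after the results were known.

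What stands is that no named analysis estimates agreement or accuracy for the comparisons in groups 1 to 4.

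**Conclusion.** The concern holds for the comparisons in groups 1 to 4 and must be fixed. Followed as written, the plan cannot support a conclusion that USG is reliable against MR or across probe, angle and frequency settings. The fault lies in the listed analyses; it would be too strong to infer that the data could never answer the question.

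The central finding comes from setting the aim beside the list of tests and needs no assumed figure. The illustrations rest on 25 volunteers per group, normal data and, where a shift or absolute limits are quoted, the plan's SD of 0.05. Correlation 0 and kappa −0.60 are deliberate extremes. That each volunteer is measured under every setting being compared is the natural reading of RESEARCH METHOD, but the document does not say so outright. Some pages of the form were not available for this review; the statistics section itself appears complete.

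**What to change.** Revise the statistics section as follows.

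1. **Groups 2 to 4, and any quantity measured on both USG and MR in group 1.** Make Bland-Altman limits of agreement with 95% CIs the main analysis for each pair of settings, with an absolute-agreement ICC in support. Allow for two sides per volunteer. Use paired, not independent-sample, tests as secondary analyses of mean shift.
2. **Group 1.** Define before analysis which USG and MR findings are compared. For categorical disc and soft-tissue findings, where the protocol's rationale treats MR as the reference, report sensitivity, specificity and kappa with CIs that account for two joints per volunteer.
3. **Functional examination.** Keep the between-group tests where USG values are compared between volunteers with and without a clinical finding, and add an effect estimate with 95% CI. Use kappa only where both are categorical on the same scale.
4. **Interpretation.** State that p > 0.05 will not be read as agreement, and that accuracy estimates apply to symptomatic patients, the only ones recruited.

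The cost is new wording, written definitions and some extra analysis, with no new volunteers or USG scans. The price is visible imprecision, as in step 6 of the working. Group 1 is limited to what the existing MR records contain; re-reading the images would take reader time. The interval between MR and USG is not stated, so some disagreement there may reflect change over time.

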## SAMPLE INFORMATION

How was the number of volunteers to participate in the research determined? Explain	When calculating the sample size of our study, reference values in previous similar studies were taken into consideration. When similar dental studies are examined; ( $\mu_1 - \mu_2$ ) and sd values are seen to range from 0.01 to 0.05 (Odacı E. v.d, 2003). When determining the sample size of the study ( $\alpha=0,05$ , $1-\beta=80\%$ ) $f(\alpha, \beta)=7,85$ , $sd =0,05$ and ( $\mu_1 - \mu_2$ ) = 0,02 when taken, it is seen that the sample size is $n = 100$ . It is planned to include 100 volunteers in our research.
Sampling method	Volunteers will be selected from patients who applied to our clinic and who have complaints of temporomandibular joints.

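### For continuous variables the plan names only independent two-sample tests, with no method for comparisons over more than two groups or over several MHz settings in the same volunteers

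*Combined protocol and SAP*

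**What the plan says.** The section on statistical methods gives one rule for normally distributed continuous data, "Difference evaluations of continuous variables between groups will be made with Student's t test in data with normal distribution", and one for the rest, "Group comparisons for data that are not suitable for normal distribution will be performed with Mann Whitney U test". For categorical variables, "the Chi-Square test will be used to look for a difference between the groups". It names no ANOVA, Kruskal-Wallis, paired, repeated-measures or Friedman method and no adjustment for multiple comparisons. It does not define which groups it means.

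The Research Method section says "Volunteers to participate in the research will be divided into 4 groups". Each group has its own question: ultrasound against MR (I), linear against hockeystick probe (II), horizontal against longitudinal angle (III), and probe frequency (IV). On the last: "In volunteers in group 4, the megahertz values of the probe are changed and the findings obtained by examining them separately will be compared". The number of frequencies is not given. The groups are to be evaluated separately, after which the ultrasound data of all four are compared with the functional joint examination. The number of categories of the functional findings is not given either.

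The only significance level in the document is the 0.05 used under Sample Information, where "It is planned to include 100 volunteers in our research".

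**The concern.** Student's t and Mann-Whitney U each compare two independent samples. The protocol leaves room for continuous comparisons with more than two levels in three places: groups I to IV, functional findings with three or more categories, and group 4 with three or more frequencies. An analyst following the text could cover these only by running the named tests pair by pair, with no overall test in front of them and no adjustment.

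Two different harms follow. Across independent groups, the 5% level no longer limits the chance of a false finding for the outcome as a whole. Across settings read in the same volunteers, an unpaired test ignores the pairing and can miss a real difference between settings, which is what group 4 is meant to detect.

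The volunteers contribute eight continuous readings each: joint interval right and left, mouth open and closed (4), and masseter thickness right and left, free and tight closing (4). The problem can recur for each of them.

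**Working it through.** **Inputs from the protocol.** Significance level 0.05, power 80%, f = 7.85, SD 0.05, difference 0.02, n = 100 (Sample Information); four groups (Research Method).

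**Assumptions.** 25 volunteers per group, because group sizes are not stated; normal data with equal variances; within-person correlations of 0.3, 0.5 and 0.8; two to four MHz settings.

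**The plan's own figure.** f = (1.960 + 0.842)² = 7.85, so the level is two-sided. The two-sample formula gives 2 × 7.85 × (0.05/0.02)² = 98.1 per group, which matches the stated 100 after rounding. The sample size therefore also rests on a single contrast of two independent groups. (That it reproduces as a per-group number while 100 is the total enrolment is a separate matter.)

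**More than two independent groups.** With k groups there are k(k − 1)/2 pairs: 6 for k = 4 and 3 for k = 3. When all means are equal, at least one pair has p < 0.05 if the studentized range exceeds 1.96 × √2 = 2.77. In large samples:
- k = 3: 12.2%
- k = 4: 20.3%

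Simulation with 25 per group gives 11.9% for three groups with t tests. For four groups it gives 20.2% with t tests and 19.1% with Mann-Whitney. The assumed group size therefore hardly matters. If the six tests were independent the figure would be 1 − 0.95⁶ = 26.5%. It is lower because pairs share groups.

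**MHz settings in the same volunteers.** With correlation ρ between settings, the mean difference has variance 2σ²(1 − ρ)/n, but the unpaired test assumes 2σ²/n. Its statistic is thus too small by a factor of about √(1 − ρ). For two settings at ρ = 0.5, the effective critical value is 1.96/0.707 = 2.77, an error of about 0.6%.

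Simulated chance of at least one false positive over all pairs, 25 volunteers, unpaired t tests:

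| Correlation | 2 settings | 3 settings | 4 settings |
|---|---|---|---|
| 0.3 | 2.0% | 5.1% | 9.5% |
| 0.5 | 0.7% | 1.9% | 3.7% |
| 0.8 | <0.1% | <0.1% | <0.1% |

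Unadjusted paired t tests on the same data give about 5%, 12% and 21% for two, three and four settings.

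**Loss of power.** For two settings, a true shift of 0.4 SD and correlation 0.8 (both assumed), 25 volunteers give about 13% power with the unpaired test and about 85% with the paired test.

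**The case against.** The strongest reply is that the protocol never plans to test groups I to IV against one another. Each group has its own question, the groups are evaluated separately, and groups I to III each compare two named levels. The phrase about differences between groups may be generic. The functional findings could be two-category, and there could be only two frequencies. This stands in part: a contrast among I to IV is an inference, so the 20% is conditional. It does not repair the plan, because the statistical section offers no other inferential method for continuous data, and nothing limits the functional findings or the frequencies to two levels.

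The design is also marked as descriptive, so strict family-wise control can be seen as partly a matter of preference. That tempers the urgency. It does not touch the mismatch between unpaired tests and repeated readings.

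Three stronger readings are tempting and are not supported:
- A reader might infer that the study's false-positive rate is 20% instead of 5%. That figure is the chance of at least one false positive per outcome if all four means are equal and all six pairs are tested. Each single test stays at 5%.
- A reader might carry the 12% over to three MHz settings. The settings are compared within group 4 volunteers, and the unpaired tests the plan names would usually err in the conservative direction there.
- A reader might conclude that nothing in the plan handles four groups. Chi-square does, for categorical variables. The gap concerns continuous variables.

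**Conclusion.** The concern holds for continuous variables, in conditional form. Where an outcome is compared over more than two independent groups, the plan as written leads to unprotected pairwise testing, with a family-wise error per outcome of about 20% for four groups and 12% for three. These figures assume all means equal and all pairs tested, and they barely depend on group size.

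For MHz settings read in the same volunteers, the named tests are generally conservative at moderate to high correlation (about 2% over three settings at 0.5) and lose power. At a low correlation of 0.3 this protection fades: about 5% for three settings and 9.5% for four. With only two settings there is one test and no multiplicity, but the unpaired test is still the wrong one. The correlations, the 25 volunteers and the number of settings are assumptions. The change should be made, though nothing here shows that any particular planned comparison is invalid.

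**What to change.** In the statistical methods section, replace the two sentences on continuous variables with rules by type of comparison:
- **More than two independent groups:** one-way ANOVA with Tukey-adjusted pairs, or Kruskal-Wallis with Dunn-adjusted pairs if the data are not normal.
- **More than two settings in the same volunteer:** a repeated-measures or mixed model, or the Friedman test, with adjusted pairs.
- **Two settings in the same volunteer:** paired t test or Wilcoxon signed-rank test.
- **Two independent groups:** Student's t or Mann-Whitney U, as now.

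State alongside which groups are compared with which, how many MHz settings are used, and how many categories the functional findings have, so that each comparison falls under one rule before the data are seen.

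The cost is wording only; these are standard SPSS procedures. The small downside is that single pairwise differences between independent groups will be declared significant less often.

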**RESEARCH BUDGET**

Total research expenses	***** TRY
Source of research expenses	
	 The researcher himself
	 Supporting
X	 University (Scientific Research Projects Unit)
	 TÜBİTAK
	 DPT
	 Industry and Other Institutions

**CENTERS PARTICIPATED IN THE RESEARCH**

X	 Single Center
	 Multi Center

## PLANNING TIME OF THE RESEARCH:

■ Planned Start Date: 01.01.2020
■ Planned End Date : 01.01.2021

